4.1.5 Inclusion of data in summaries at patient level

For summaries at a patient level, all values will be included, regardless of whether they appear in a corresponding visit based summary e.g. when deriving a patient level statistic such as a worst (maximum or minimum) value.

4.1.6 Descriptive statistics

Descriptive statistics will be used according to the variable's measurement scale.

Descriptive statistics for continuous variables

Continuous variables (except those with censoring) will be summarised by

- the number of observations (n), mean, SD, minimum, 1st quartile, median, 3rd quartile and maximum (if the quartiles are being included)
- the number of observations (n), mean, SD, median, min, max (if the quartiles are being excluded).

For original variables (i.e., variables not derived), the mean, 1st quartile, median and 3rd quartile will be rounded to 1 additional decimal place compared to the original variable; the SD will be rounded to 2 additional decimal places compared to the original variable. Minimum and maximum will be displayed with the same number of decimals as the original variable.

[figure not shown]
For derived variables, the number of decimals will be determined in the Analysis Datasets Specification; subsequently the rule above will be applied.

Boxplots

Boxplots may be used to illustrate important distribution characteristics for continuous variables. Figure 3 below illustrates the boxplot elements. If boxplots will be provided for several measurements (e.g., visits) over time, then the means or medians for the same treatment arm will be connected. If more than one treatment arm is displayed within a figure, then the

treatment arms will be distinguished by different colours and different line styles connecting mean/medians over time.

Figure 3 **Boxplot elements**

By default, individual values are marked if there are any above the upper fence (as shown in Figure 3 above) or below the lower fence (not the case in Figure 3 above). If, however, the display of such extreme values would bring the entire figure out of scale (e.g., a comparison of boxes across time or treatment group would hardly be feasible), then the option to not display such extreme values can be discussed with AstraZeneca.

Frequency tables for categorical variables

Categorical variables will be summarised by frequency counts and percentages for each category. Percentages will be calculated using the number of observations with non-missing values as the denominator. As an exception, frequency tables displaying categorical demographics and baseline disease characteristics will include the number of missing observations in the denominator for calculating percentages.

A missing category shall be included only for categorical variables where any records with missing values are available; this case only the number of missing values will be displayed but not percentages. The missing category will be omitted if there were no missing values for that variable.

Kaplan-Meier figures for right-censored time to event variables

Survival functions are of interest for right-censored time to event variables (in this study for PFS and OS). These will be estimated by Kaplan-Meier (KM) product limit estimators and plotted over time (called “KM curves”) with SAS PROC LIFETEST. Treatment arms will have different colour / line styles and censored observations will be marked. At the bottom of KM figures the number of patients still at risk at baseline Week 8, 16, 24, etc will be displayed for each treatment arm.

Summaries of the number and percentage of patients who have died, those still in survival follow-up, those lost to follow-up and those who have withdrawn consent will be provided for each treatment arm. If estimable, median time to event and 2-sided 90% confidence intervals (CIs) according to Brookmeyer and Crowley 1982 will be provided for each treatment arm.

4.1.7 Data listings

Data listings will not be produced for every single data domain but only for those required from a regulatory and AZ perspective according to AZ CSR Appendix 12.2 Global Specification.

Data listings will:

- display all values contributing to a time point for a patient and will highlight the value used in the summary table where appropriate
- be presented and sorted by randomised treatment arm (by actual treatment arm for safety listings), subject identifier, visit and date as appropriate.

4.1.8 General principles for statistical modelling and hypothesis testing

All statistical tests will be pairwise, i.e. comparing two treatment arms and there will be no “overall” tests of global null hypotheses (same distribution in all three treatment arms).

Any stratification in the statistical modelling will be based on the values entered into Interactive Voice Recognition System (IVRS) at randomisation, even if it is subsequently discovered that these values were incorrect. In case of at least 10% of mis-stratified patients (across all strata), a sensitivity analysis will be carried out using the (correct) baseline data collected in the eCRF.

Results of statistical analyses will be presented using 2-sided 90% CIs and 2-sided p-values for pairwise comparisons between

- AZD6738+Olaparib versus Olaparib monotherapy
- AZD1775+Olaparib versus Olaparib monotherapy
- and AZD6738+Olaparib versus AZD1775+Olaparib (as secondary analysis).

Two-sided p-values will be presented using 3 decimal places for all values ≥ 0.001 . The only categorical presentation to be used is when $p < 0.001$.

The types of statistical test(s) used to generate p-values or CIs, together with details of any stratification or prognostic factors, should be included in a footnote to the presentation or in

the text as appropriate. Any ‘post-hoc’ analyses (i.e., not pre-specified) will be clearly indicated on any outputs either by using the titles or footnotes as appropriate.

Primary statistical analyses comparing PFS based on BICR for each combination treatment arms to Olaparib will be conducted for the 3 patient populations *BRCAm*, Non *BRCAm* *HRRm* and Non *HRRm*.

Comparisons of PFS based on BICR for each of the combination treatment arms to Olaparib in the 2 patient populations *HRRm* and All will be conducted as secondary statistical analyses.

Secondary outcome measures will be analysed for the 3 patient populations *BRCAm*, Non *BRCAm* *HRRm* and Non *HRRm*, except

- ORR and OS, which will be analysed for all 5 patient populations
- Tumour and germline mutation status, which will be analysed only for the All patient population
- PK outcome measure $C_{\min,ssss}$, which will be analysed only for the All patient population

RECIST-based primary and secondary outcome measures based on Investigator assessments will also be analysed for sensitivity purposes.

Safety outcome measures and exploratory outcome measures will be analysed for the All patient population only, except

- selected AE summary tables, which will also be provided for the 3 primary patient populations
- **CCI**, which will be analysed for all 5 patient populations.

4.2 Analysis Methods

4.2.1 Handling of multiplicity

Multiplicity adjustment will be considered within each of the 3 primary patient populations for PFS. The overall 2-sided alpha for each primary patient population will be 0.2, and a simple Bonferroni adjustment assigns 2-sided alpha of 0.1 to each of the 2 pairwise treatment arm comparisons to Olaparib monotherapy.

No further adjustments for multiplicity are planned, in particular no adjustments for interim analyses.

4.2.2 Overview of timings of interim and final analyses

For the non *HRRm* population an interim futility analysis will be triggered when 75 patients have been recruited and assessed for at least 8 weeks, in order to assess the proportion of patients with Non Progressive Disease (NPD), based on the Investigator assessment at 8 weeks in each of the treatment arms. Recruitment will be paused after the 75th patient has been recruited into this patient population, until the AZ URC confirms which treatment arms should be reopened. In April 2019, the AZ URC determined that recruitment to the AZD1775+olaparib arm should not be reopened. This parallels the ISRC recommendation to close recruitment to the AZD1775+olaparib arm in all three populations for safety concerns.

A further NPD futility interim analysis in the non *BRCAm* HRR*m* population may be performed, if the outcome of the interim analysis in the non HRR*m* population resulted in treatment arms being stopped.

For each of the 3 primary patient populations (*BRCAm*, non *BRCAm* HRR*m*, non HRR*m*) a further interim analysis for PFS is triggered when 44PFS events for the AZD6738+olaparib vs. olaparib monotherapy pairwise comparison in that particular patient population have occurred. As the non HRR*m* patient population is expected to be enrolled quicker than the other patient populations, it is expected the interim analysis for this patient population will occur first, followed by interim analysis for the 2 other primary patient populations. These PFS interim analyses may be concurrent or separate depending on the recruitment and PFS event rates for the 3 patient populations and other operational requirements.

For each of the 3 primary patient populations (*BRCAm*, non *BRCAm* HRR*m*, non HRR*m*) the final analysis for PFS is triggered when 68 PFS events in that particular patient population have occurred. These final analyses may be concurrent or separate depending on the recruitment and PFS event rates for the 3 patient populations and other operational requirements.

An initial OS analysis will be performed at the same time as the primary analysis of PFS. A further analysis of OS will be performed when the OS data for the AZD6738+olaparib vs. olaparib monotherapy pairwise comparison are approximately 70% mature.

4.2.3 General time-to-event analysis considerations

Stratification of log rank test and proportional hazards model

Time-to-event endpoints will be analysed using stratified log-rank tests for generation of the p-value and using the Breslow approach for handling ties (Breslow 1974). Hazard ratios and their CIs will be estimated from stratified proportional hazards models (with ties = Efron) and the CIs calculated using a profile likelihood approach. For both approaches, the stratification variables will be included in the STRATA statement of SAS PROC LIFETEST and SAS PROC PHREG, respectively.

Where applicable, stratification factors will be those used in the randomization. It is sensible to have at least 5 events in each stratification cell (combination of the marginal strata). One stratification factor with 2 levels and 3 treatment arms would lead to $2 \times 3 = 6$ stratification cells. Two stratification factors with 2 and 3 levels, respectively, and 3 treatment arms would lead to $2 \times 3 \times 3 = 18$ stratification cells. If the minimum of 5 events in each stratification cell is not reached, then also unstratified analyses will be conducted.

Proportionality assumption

The assumption of proportional hazards will be examined by plots of log-log (event times) versus log (time). If these raise concerns, by fitting a time dependent covariate (adding a treatment-by-time or treatment-by-log(time) interaction term) to assess the extent to which this represents random variation. If a lack of proportionality is evident, the variation in treatment effect can be described by presenting piecewise HR calculated over distinct time-periods (0-16 weeks, 16-32 weeks, 32-48 weeks, etc).

4.2.4 PFS primary analyses based on BICR for patient populations *BRCAm*, *non BRCAm HRRm* and *non HRRm*

The study treatment status at progression of patients at the DCO date used for analysis will be summarised. This will include

- the number (%) of patients who were on study treatment at the time of progression
- the number (%) of patients who discontinued study treatment prior to progression
- the number (%) of patients who have not progressed and were on study treatment
- the number (%) of patients who have not progressed and discontinued study treatment.

Primary analyses of PFS will be based on data from the BICR and conducted separately for the patient populations *BRCAm*, *non BRCAm HRRm* and *non HRRm*, respectively.

In each of these 3 patient populations, PFS will be analysed using pair-wise log rank tests stratified for prior platinum-based therapy (no, yes) for generation of the p-value. Pairwise HRs and two-sided 90% CIs will be estimated from a proportional hazards model stratified for prior platinum-based therapy (no, yes). The two-sided 80% and 60% CIs will also be estimated.

For each of these 3 patient populations, KM curves for PFS will be presented by treatment arm, overall and separately by prior platinum-based therapy (no/yes).

The number of events, median PFS with two-sided 90% CIs, and the percentage PFS as well as two-sided 90% CIs at 3, 6, 12, 18 and 24 months will be summarised. For calculating these CIs:

- KM estimates will be transformed to an unrestricted range by the $\log(-\log(x))$ function
- calculation of CIs by applying normal approximation methods to the transformed scaled
- re-transformation of CIs to the original scale.

This approach is triggered by option `CONFTYPE=LOGLOG` in SAS PROC LIFETEST.

The progression status at the time of the PFS analysis will also be summarised, including the number and percentage of patients who progressed due to RECIST progression (separately for TLs, NTLs and new lesions) or due to death, or did not progress due to being progression free or due to being lost to follow up or due to withdrawn consent.

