- l All patients must receive a 5-HT3 antagonist, ondansetron (Zofran) 8 mg PO or granisetron (Kytrel) 1 mg orally prior to each dose of AZD1775. Additional doses of 5-HT3 antagonist may be used if needed. In addition, dexamethasone 4 mg orally will be given with each AZD1775 dose as a minimum on the first day of dosing AZD1775 of every 3 days dosing period, unless contraindicated or not well-tolerated. Dexamethasone may be continued on further days of dosing, potentially at a lower dose. Dexamethasone or the 5-HT3 antagonist may be given by IV. Promethazine (Phenergan), prochlorperazine (Compazine), and benzodiazepine may still be used as additional adjunctive treatments during AZD1775 therapy. **Please note: aprepitant [E-mend] and fosaprepitant are not permitted due to known DDIs. No longer applicable following CSPv6.0, provided there has been a minimum washout period of 10 days since the final dose of AZD1775.** Patients should be strongly encouraged to maintain liberal oral fluid intake.

- m **CCI** sample should be taken at same visit as scan, if possible. If a **CCI** sample was taken at a scan visit not coinciding with the CxD1 visit a **CCI** sample at the CxD1 visit is not required
- n Scan visit may be tied in with CxD1 visit, using ± 7 d window, if appropriate
- o Unscheduled D8 and D15 visits with complete blood counts should be done from C3 onwards if Grade 3/4 neutropenia, G4 thrombocytopenia or a dose interruption due to haematological toxicity was experienced in a prior cycle. If no further events are experienced in the subsequent 3 consecutive cycles, then the Day 15 CBC visit can be stopped. **No longer applicable following CSPv6.0.**
- p The pharmacogenetic blood sample can be obtained either at the first treatment visit or after randomisation

* Please note that cycle length for AZD1775+olaparib treatment arm is 21 days.

** Please note that for patients on the AZD1775+olaparib treatment arm, the continuous olaparib dose will be 200 mg bd. After April 2019, all patients randomised to this treatment arm discontinued AZD1775 and were offered the opportunity to continue olaparib monotherapy at 300 mg bd on a 21-day cycle starting at the patient's next treatment cycle to ensure a minimum 10 day wash out period from AZD1775 to olaparib monotherapy 300 mg bd dosing to avoid DDI.

PBMC=peripheral blood mononuclear cell

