5.1 Efficacy assessments

5.1.1 CT and MRI scans; Tumour assessments (RECIST 1.1)

Following the baseline assessment, subsequent tumour assessments according to RECIST 1.1 should be performed every 8 weeks (± 1 week) for the first 72 weeks and then every 12 weeks (± 1 week) thereafter, relative to the date of randomisation and irrespective of treatment decisions, up to objective disease progression by RECIST 1.1.

The imaging modalities used for RECIST 1.1 assessment will be CT scans of the chest, abdomen and pelvis (or MRI where CT is contraindicated) with other regions as clinically indicated for the assessment of disease. Brain CT scan/MRI at baseline should be done for patients with known history of brain metastatic disease. Any other sites at which new disease is suspected should also be appropriately imaged. The methods of assessment of tumour burden used at baseline must be used at each subsequent follow-up assessment.

Radiological examinations performed in the conduct of this study should be retained at site as source data.

Coded copies of all scans, regardless of modality, are to be sent to an AstraZeneca appointed CRO for BICR.

All treatment decisions will be based on site assessment of scans. After the primary PFS analysis for each of the strata, central review of scans will no longer be required for that stratum and Investigators will be advised when to stop sending copies of the scans to the CRO conducting the central review. Patients who are determined to have progressed according to RECIST 1.1 criteria by the Investigator will have scans centrally reviewed for confirmation of objective disease progression. If disease progression is not confirmed at central review an additional RECIST 1.1 assessment may be requested preferably at the next scheduled RECIST 1.1 visit, if the central assessment is available in an appropriate timeframe.

It is important to follow the assessment schedule as closely as possible. If scans are performed outside of scheduled visit ± 1 week window interval and the patient has not progressed, every attempt should be made to perform the subsequent scans at their scheduled time points. Patients will be evaluated until objective radiological disease progression by RECIST 1.1 as per the study schedule (see [Table 3](#), and [Table 4](#) and [Table 5](#)), and then followed for survival, regardless of whether study treatment is discontinued or delayed and/or protocol violations, unless they withdraw consent.

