5.1.2 Tumour evaluation

RECIST 1.1 criteria will be used to assess patient response to treatment by determining PFS times and ORRs as appropriate to study endpoints. The RECIST 1.1 guidelines for measurable, non measurable, target and non target lesions and the objective tumour response criteria (CR, PR, SD or progressive disease [PD]) are presented in [Appendix F](#).

The methods of assessment of tumour burden used at baseline - CT or MRI scans of chest, abdomen, and pelvis (as well as brain CT scan/MRI for patients with known history of brain metastatic disease) must be used at each subsequent follow-up assessment. Any other areas of disease involvement should be additionally imaged based on the signs and symptoms of individual patients.

Following the baseline assessment, efficacy for all patients will be assessed by objective tumour assessments every 8 weeks until Week 72 and every 12 weeks thereafter until objective disease progression as defined by RECIST 1.1. Any other sites at which new disease is suspected should also be appropriately imaged.

If a patient discontinues treatment (and/or receives a subsequent cancer therapy) prior to progression then the patient should still continue to be followed until objective disease progression as defined by RECIST 1.1.

Categorisation of objective tumour response assessment will be based on the RECIST 1.1 criteria of response: CR, PR, SD and PD. Target lesion (TL) progression will be calculated in comparison to when the tumour burden was at a minimum (ie, smallest sum of diameters previously recorded on study). In the absence of progression, tumour response (CR, PR, SD) will be calculated in comparison to the baseline tumour measurements obtained before starting treatment.

Following progression, patients should continue to be followed up for survival approximately every 8 weeks as outlined in the study plan.

It is important to follow the assessment schedule as closely as possible. Please refer to the study plan in [Table 3](#), [Table 4](#) and [Table 5](#).

Following the final PFS analysis data cut off for each stratum (either non HRR*m*, BRC*Am* and/or non BRC*Am* HRR*m*) objective tumour assessments should be performed as per the study schedule (see [Table 3](#), [Table 4](#) and [Table 5](#)) for patients continuing on treatment and recorded in the patient notes **but not** recorded in the eCRF.

Central reading of scans

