3.3 Primary outcome measure (derivation of efficacy variables)

3.3.1 Progression-free survival

PFS is defined as the time from randomisation until the date of objective disease progression or death (by any cause in the absence of progression) regardless of whether the patient withdraws from randomised therapy or receives another anti-cancer therapy prior to progression. PFS for patients who have not progressed or died at the time of analysis will be censored at the latest date of assessment from their last evaluable RECIST assessment.

PFS will be computed as date of PFS event or censoring – date of randomisation + 1).

If, however, a patient progresses or dies after two or more missed scheduled RECIST assessments, the patient's PFS will be censored at the time of the latest evaluable RECIST assessment prior to the two missed visits.

The allowed gap between the last previous evaluable RECIST assessment and the tumour progression or death, for which the tumour progression/death will still be counted as an event, will be defined as 2 x (scheduled time between scans + allowed visit window). In details:

- If the two missed visits will occur immediately after the baseline scan then the definition of two missed visits will be calculated as 2 x (the protocol-scheduled time between scans) + the protocol-allowed visit window (since there is no need to account for an early initial visit in this case) which will be 2 x 8 weeks + 7 days + patient-specific number of days from date of randomization to date of first study treatment dose = 119 days + (patient-specific date of first study treatment dose minus date of randomization).
- If the two missed visits will occur after a post-baseline scan then the definition of two missed visits will be 2 x (the protocol-scheduled time between scans + the protocol-allowed visit window) since the previous scan may be 1 week earlier than planned and the progression visit may be 1 week later than planned.
- While a patient is in the every-8-weeks-schedule, the definition of two missed visits will be 2 x (8 weeks + 7 days) = 126 days.
- When a patient is changing from the every-8-weeks-schedule to the every-12-weeks-schedule, the definition of two missed visits will be 8 weeks + 12 weeks + 14 days = 154 days.
- While a patient is in the every-12-weeks-schedule, the definition of two missed visits will be 2 x (12 weeks + 7 days) = 182 days.

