If a patient has no evaluable visits or does not have baseline data they will be censored at Study Day 1 unless the patient dies within 17 weeks (16 weeks for two potential scans plus 1 week allowing for a late assessment within the visit window) + (patient-specific date of first study treatment dose minus date of randomization).

The PFS time will always be derived based on scan/assessment or death dates, not on visit dates. RECIST assessments/scans contributing towards a particular visit may be performed on different dates. The following rules will be applied:

- For BICR assessments, the date of progression will be determined based on the **earliest** of the scan dates of the component that triggered the progression for the adjudicated reviewer

selecting PD or of the reviewer who read baseline first if there is no adjudication for ICR data.

- For site investigator assessments, the date of progression will be determined based on the **earliest** of the dates of the component that triggered the progression.
- For both ICR and site investigator assessments, when censoring a patient for PFS the patient will be censored at the **latest** of the dates contributing to a particular overall visit assessment.

For TLs only the latest scan date is recorded out of all scans performed at that assessment for the TLs and similarly for NTLs only the latest scan date is recorded out of all scans performed at that assessment for the NTLs.

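### Minor: the piecewise PFS hazard-ratio periods are cut on scheduled scan weeks, so arm-different scan timing could create a false time pattern; mid-interval cuts avoid most of this at no cost.

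*SAP*

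**What the plan says.** SAP 4.2.3 examines proportionality with log-log plots and, if these raise concerns, a time-dependent treatment term. The next step is conditional and permissive: "If a lack of proportionality is evident, the variation in treatment effect can be described by" separate hazard ratios for successive periods. The section names those periods as follows: "presenting piecewise HR calculated over distinct time-periods (0-16 weeks, 16-32 weeks, 32-48 weeks, etc". It does not say which period holds the boundary day.

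The scan schedule and the dating of PFS are set elsewhere:

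- Protocol 5.1.2 requires "tumour assessments every 8 weeks until Week 72 and every 12 weeks thereafter". Protocol 5.1.1 times the scans "relative to the date of randomisation and irrespective of treatment decisions", within one week either side.
- SAP 3.3.1 uses the same window in its missed-visit rule: "2 x (8 weeks + 7 days) = 126 days".
- SAP 3.3.1 also states: "The PFS time will always be derived based on scan/assessment or death dates, not on visit dates". PFS is the event date minus the randomisation date, plus 1.
- Protocol 4.2 gives 28-day cycles for olaparib and ceralasertib+olaparib, and 21-day cycles for the AZD1775 arm.
- Protocol Table 5, footnote n, says of the AZD1775 arm: "Scan visit may be tied in with CxD1 visit", using a 7-day window, if appropriate.

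**The concern.** Each of the three named cuts falls in the middle of a scan window. Suppose a progression is found at the Week 16 scan. If the scan is a few days early, the event counts in the first period; if a few days late, in the second. This does not apply to progressions found at Weeks 8, 24 or 40.

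The piecewise HRs are produced when readers ask when the effect occurs. If one arm tends to be scanned earlier than the other, events shift across the cut in one arm only, and the period HRs can show a time pattern where the true HR is constant.

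Elsewhere the SAP avoids this. Section 4.1.4 ends each post-baseline visit window half way to the next visit, which puts the scan-window boundaries in Table 4 at 84 and 140 days after Dose Day 1 (Weeks 12 and 20). The landmark times in 4.2.4 (3, 6, 12, 18 and 24 months) also fall between scans.

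**Working it through.** **Model inputs.** The plan states no figure for the piecewise HRs. Its sample-size figure was reproduced first, to confirm the survival assumptions. With 1:1 allocation and two-sided alpha 0.10, the Schoenfeld formula is events = 4(1.645 + 0.842)² / (ln HR)². The stated medians of 6 and 11 months imply HR = 6/11 = 0.545, which gives 67.3, so 68 events, as planned.

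**Where the cuts fall.** Scans are due at Weeks 8, 16, 24, … 72, then 84, 96 and so on.

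- The cuts at 16, 32 and 48 are all scan weeks. Continued in 16-week steps, 64 and 96 are too; 80 is not.
- 16 weeks = 112 days. On the PFS scale an on-time Week 16 scan is 112 + 1 = Day 113, one day past the cut, and its window is Days 106-120.
- If scans spread evenly over those 15 days, 7/15 = 47% fall on or before Day 112.
- About 37-38% of events up to Week 72 are first detected at the Week 16, 32 or 48 scan. This assumes exponential PFS, a control median of 5-6 months, HR 0.55-1 and all events found by scan.

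**Timing allowed in the AZD1775 arm.** Cycle Day 1 visits fall on Day 1 + 21k. Those within 7 days of Days 57, 113, 169, 225, 281 and 337 are Days 64, 106, 169, 232, 274 and 337. Tied scans therefore come a week before the Week 16 cut and a week after the Week 32 cut. With 28-day cycles, Day 1 + 28k gives Days 113, 225 and 337 exactly.

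**Simulation.** Exponential PFS, control median 5 months, period-specific Cox model with Efron ties, large samples. Period HRs when the true HR is 1 throughout:

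| Scan timing | Cuts 16/32/48 | Cuts 12/28/44 |
|---|---|---|
| Same in both arms, even over ±7 days | 0.99 / 1.00 / 1.01 | 0.99 / 1.01 / 1.00 |
| One arm later by 2 days on average (−5 to +7 vs −7 to +5) | 0.92 / 0.97 / 0.98 | 1.01 / 0.94 / 0.95 |
| One arm later by 4 days on average (−3 to +7 vs −7 to +3) | 0.81 / 1.02 / 1.02 | 1.02 / 0.92 / 0.92 |
| AZD1775 scans all tied to 21-day cycles, comparator on the exact day | 1.59 / 0.51 / 0.91 | 0.99 / 0.96 / 0.91 |

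If all AZD1775 scans are tied but comparator scans are spread over the window, the first two periods with the SAP's cuts are about 1.2 and 0.6 (separate runs gave 1.17/0.57 and 1.12/0.51).

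At the design HR of 0.55, the tied worst case gives 0.91 / 0.30 / 0.51 with the SAP's cuts and 0.57 / 0.53 / 0.51 with mid-interval cuts. The 2-day case gives 0.51 / 0.54 / 0.56 and 0.56 / 0.54 / 0.54.

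**Precision in one trial.** With 68 events and true HR 1, about 31 fall in weeks 0-16. SE(log HR) is about 2/√31 = 0.36, so the 90% CI around 0.92 is 0.92 × exp(±1.645 × 0.36), or roughly 0.51 to 1.66. Over 1,500 simulated trials of 50 per arm, a first-period HR below 1 followed by one above 1 occurred in 26.8% with equal timing and 30.0% with the 2-day difference.

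**The case against.** The strongest case against acting is that this output matters little, and much of that case stands.

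- **It is conditional.** Piecewise HRs appear only after plots and an interaction term suggest non-proportionality. In 300 simulated trials at 50 per arm with true HR 1, tied scans did not make this more likely: the treatment-by-log(time) term reached p<0.10 in about 9%, against about 10% with identical schedules.
- **The live comparison is barely exposed.** The study is now sized only for ceralasertib+olaparib versus olaparib. These arms share cycle length and scan schedule, and nothing in the documents suggests that one is scanned later. The 2-day delay is an assumption.
- **The large figures are a worst case in a closed arm.** Footnote n permits tying and does not require it. The direction also depends on a one-day convention: without the +1 and with no dosing lag, the tied case gives 0.94 / 0.62 / 1.71.

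A reader might infer that piecewise HRs are the plan's only account of the effect when proportional hazards fails. They are not: SAP 4.2.4 always reports Kaplan-Meier curves, medians and PFS percentages at five landmarks. Piecewise HRs are only the specified way of showing how the HR itself changes over time.

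The evaluation-time-bias analysis in SAP 4.2.5 does not answer the point fully. Its progression midpoints serve the overall test and HR, not the period HRs. Its summaries of inter-assessment times by arm would, however, help to reveal a difference in timing.

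**Conclusion.** The point holds as a minor one. The cuts sit on scan weeks and PFS follows actual scan dates, so scan timing allocates part of the events to periods. Bias arises only if timing differs between arms.

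In the main comparison the effect is small: about 0.92 for a true HR of 1, under an assumed 2-day delay and well inside the sampling error of one period. In comparisons with the AZD1775 arm, which are still planned, it could be large: about 1.5 then 0.5 at worst, and about 1.2 then 0.6 with comparator scans spread over the window.

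A reader might go further and expect a false reversal of effect in the main comparison, or doubt the primary result. The documents support neither. With equal timing there is no systematic bias. At the design HR of 0.55 the large-sample period HRs stayed below 1 in every scenario run. The primary log-rank test and overall HR do not use the periods.

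The figures assume exponential PFS, all events found by scan, no dropout and the stated timing patterns. Deaths and OS are unaffected.

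**What to change.** In SAP 4.2.3, for PFS only, replace the example periods with ones that end midway between scheduled scans: 0-12, 12-28, 28-44, 44-60 weeks, and so on. After Week 72 use midpoints of the 12-week schedule, the first being (72 + 84)/2 = Week 78. Each period then holds whole scan visits with their windows. State also which period contains the boundary day. OS periods can stay as they are.

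This removes most of the artefact in the tied-scan case. It does not remove the effect of later detection itself: under the 2-day delay the later periods still read 0.94-0.95, so the gain in the main comparison is slight.

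The cost is one sentence in the SAP and different cut points in the same programs. No new data or protocol change is needed. Fixing the cuts before unblinding also avoids a post-hoc choice.
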